#### **Archival Tumor Tissue Samples**

Archival tumor biopsy samples can be obtained from the FFPE tissue block or FFPE unstained slides. Formalin-Fixed Paraffin-Embedded archival tumor biopsies must meet the following criteria to be an acceptable sample:

• With the exception of the archival sample from first diagnosis, the FFPE tissue tumor blocks must have been obtained within ≤ 4 months of the first dose of study intervention. Of note, the participant must not have received any anti-cHL treatment within that time period otherwise fresh tissue is required.

- If archival tumor tissue FFPE blocks are not available for sectioning at screening, then archival tumor FFPE unstained slides are acceptable if sectioned less than 4 months prior to the first dose of study intervention.
  - A minimum of 10 unstained slides is required for biomarker determination and an additional 5 to 10 unstained slides for exploratory biomarker analysis.
- If archival tumor tissues are greater than 4 months prior to first dose of study intervention, then an additional fresh tumor tissues biopsy is required.

#### Fresh Tumor Tissue Samples

Fresh tumor tissue biopsies must meet the following criteria to be acceptable samples:

- Only core biopsies or excisional biopsies are acceptable. Samples from fine-needle aspiration are not acceptable.
- Part A Dose Escalation cohorts: For participants who undergo tumor biopsies at screening and/or on treatment, it is preferred, though not required, that the biopsied lesion be distinct from any target lesion used in the Modified Lugano criteria.
- Part B Dose Expansion cohorts: For participants who undergo biopsies at screening and/or on treatment, the biopsied lesion must be distinct from any target lesion used in the Modified Lugano criteria.

Time points for sample collection are presented in Table 18. For all participants in the study, additional fresh tumor biopsies may also be considered if clinically indicated and feasible, eg, at disease progression or for mixed responses or pseudo-progression.

If clinically feasible, at each fresh tumor sample time point, participants will undergo core image-guided needle biopsies. Per institutional practice, image-guided fresh core needle tumor biopsies (preferably 18 gauge or larger needle) should be preferentially obtained from tumor tissues that are safely accessible, as determined by the Investigator. If possible, sample same site for pre-treatment and C1D8 biopsies. Sites should confirm adequacy of tumor biopsy material at the time of the procedure.

#### 8.6.2.2 Non-tumor Tissue Biopsy at Toxicity

For all participants in the study who undergo non-tumor tissue biopsies (eg, skin, liver, or kidney) to evaluate toxicity, involved tissue should be biopsied if clinically indicated and feasible and following the participant's consent. Adjacent uninvolved tissue should also be biopsied if the participant consents.

Samples will be assessed for predictive and/or pharmacodynamic immune-related biomarkers associated with toxicity profile using assays, including but not limited to, IHC, multiplex immunofluorescence, RNA expression, and proteomic analyses. Details for fresh non-tumor tissue biopsy sample collection, processing, storage, and shipment are provided in the Laboratory Manual.

Note: The above collection of tissue biopsy samples is not applicable in mainland China.

# 8.6.3 Collection of Optional Biomarker Samples

Collection of optional samples for biomarker research is also part of this study as specified in the SoA (Table 1, Table 2, Table 3, and Table 4) and is subject to agreement to optional consent. Refer to Section 8.6.2 for additional details for optional tissue samples collected during the study.

Note: The above collection of biomarker samples is not applicable in mainland China.

# 8.7 Optional Genomics Initiative Sample

Collection of optional samples for Genomics Initiative research is also part of this study as specified in the SoA (Table 1) and is subject to agreement in the ICF addendum.

A saliva sample for DNA isolation will be collected from participants who have consented to participate in the genetic analysis component of the study. Participation is optional. Participants who do not wish to participate in the genetic research may still participate in the study.

See Appendix F for information regarding the Genomics Initiative genetic sample. Details on processes for collection and shipment and destruction of these samples can be found either in the appendices or in the Laboratory Manual. For storage and destruction of genetic samples see Appendix F.

Note: Optional Genomics Initiative Samples will not be collected in mainland China.

# 8.8 Health Economics/Medical Resource Utilization and Health Economics

Health Economics/Medical Resource Utilization and Health Economics parameters are not evaluated in this study.

# 8.9 Assessments for Participants Who Transition to PTAP

Participants who continue to derive clinical benefit from treatment with sabestomig per investigator assessment and are still enrolled at the time of the final DCO, will proceed with the continued planned 21-day dosing schedule of sabestomig in the PTAP for this study.

AstraZeneca will inform investigators of planned and activated PTAP initiation timelines within each country, if available. The participant's last scheduled dosing visit prior to the final study DCO will include collection of samples indicated in the SoA Table 2 in addition to planned assessments for the scheduled dosing visit, ensuring no duplicates. See Section 6.9 for further details about PTAP.

# 9. STATISTICAL CONSIDERATIONS

The statistical analyses will be performed by AstraZeneca or its representatives. A comprehensive SAP will be prepared.

# 9.1 Statistical Hypotheses

There are no planned formal statistical hypotheses to be tested in this study.

# 9.2 Sample Size Determination

Approximately 180 participants will be treated with sabestomig, with up to participants in Part A (Dose Escalation) and conparticipants in Part B (Dose Expansion). Additional participants may be enrolled if additional dose levels, expansion cohorts, treatment schedules are explored, or participants require replacement for any reason.

Note: "Enrolled" means a participant's, or their legally authorized representative's, agreement to participate in a clinical study following completion of the informed consent process. Potential participants who are screened for the purpose of determining eligibility for the study, but are not assigned in the study, are considered "screen failures" unless otherwise specified by the protocol.

#### Part A Dose Escalation

The primary objective of this study is to investigate the safety and tolerability and estimate a RP2D of sabestomig for further evaluation. Hence the number of participants has been based on the desire to obtain adequate tolerability, safety, PK, efficacy, and biological data while exposing as few participants as possible to the study intervention and study procedures.

The number of participants treated during Part A Dose Escalation will depend upon the toxicities observed as the study progresses. With participants treated at each ATD dose level (single participants each for Cohorts 1 to 4) and a maximum of participants treated at each mTPI-2 dose level (with participants each for Cohorts 5, 6, 7, and 8 [optional cohort]), up to participants may be treated for the 8 planned sabestomig dose levels (4 dose levels for ATD and 4 dose levels for mTPI-2). Additional participants may be required if additional dose levels or dosing schedules are explored. Given that the mTPI-2 algorithm leads to a dose escalation decision if there is no DLT in the first participants treated in a dose level cohort, the actual sample size evaluated may be smaller than participants.

#### Part B Dose Expansion

In Part B Dose Expansion, Col participants may be treated, which may include up to 2 cohorts, Cohorts B1 (anti-PD-1/PD-L1-exposed; col participants) and B2 (anti-PD-1/PD-L1-naïve; col participants). For analysis in Cohort B1, participants treated at the RP2D in Part A (N=col) will be combined with participants enrolled in Part B, which gives a total sample size of approximately up to 100. The sample size of col participants is primarily chosen to maintain the accuracy of a No-Go decision based on efficacy signals. Observable exact binomial two-sided 80% cIs are presented in Table 19 and Table 20.

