### 9.4.1 General Considerations

Analysis will be performed by AstraZeneca or its representatives, including CROs. A comprehensive SAP will be developed and will describe the patient populations to be included in the analyses, the analyses including any subgroup analyses or sensitivity analyses, and the procedures to account for missing, unused, and spurious data.

Data will be presented by dose level in Part A and cohorts in Part B; no direct statistical comparisons will be made between any 2 dose levels or cohorts. For Cohort B1, participants treated at the RP2D in Part A will be included.

Continuous variables will be summarized by the number of observations, mean, standard deviation, median, minimum, and maximum. Geometric mean and coefficient of variation may be presented as applicable. Categorical variables will be summarized by frequency counts and percentages for each category. Unless otherwise stated, percentages will be calculated based on the population total, by dose level or cohort and by time point as appropriate. Time to event variables will be presented using the Kaplan-Meier methodology including median time calculated from the Kaplan-Meier curves.

An interim analysis will be performed as detailed in Section 9.5.

The primary analysis for Part B will be conducted at least 3 months after the final enrolled participant has received their first dose of sabestomig.

A final analysis may be performed 6 months after the last participant begins treatment or when AstraZeneca stops the study, whichever occurs first.

SAS® version 9.4 (as a minimum) will be used for analyses presented in CSR.

Baseline will be considered the last non-missing value obtained prior to the first dose of study intervention. Any information taken after first dose of study intervention will be regarded as post-baseline information. Detailed rules for deriving baseline values are described in the SAP.

Unless stated otherwise, two-sided cIs will be produced at 95%.

As appropriate, time windows will be defined for data summaries presented by visit. Time windows are described in the SAP.

Depending on the extent of any impact, summaries of data relating to participants diagnosed with COVID-19, and impact of COVID-19 on study conduct (in particular, missed visits, delayed or discontinued study intervention, and other protocol deviations) may be generated. Further details will be provided in the SAP.

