### 9.4.2.1 Primary Endpoint(s) Objective Response Rate

The ORR is defined as the percentage of participants with a CR or PR, with the denominator defined as the number of participants in the response-evaluable analysis set.

Data obtained until progression, or last evaluable assessment in the absence of progression, will be included in the assessment of ORR, regardless of whether the participant withdraws from therapy. Participants who discontinue treatment without a response, receive subsequent anti-lymphoma therapy and then respond will not be included as responders in the ORR.

The ORR will include data of all scans, regardless of whether it was scheduled or not.

The ORR will be presented by the number and percentage of participants with a response (CR/PR) including 95% cIs based on exact binomial proportions.

Best overall response will also be summarized by n (%) for each category, with no formal statistical analysis presented.

The ORR as assessed by BICR based on Modified Lugano criteria for lymphoma is the primary efficacy endpoint in Cohort B1 in Dose Expansion. The ORR is a secondary endpoint for Part A Dose Escalation assessed by Investigator based on Modified Lugano criteria and RECIL criteria.

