#### **Complete Response Rate**

The CRR is defined as the percentage of participants with a CR, with the denominator defined as the number of participants in the response-evaluable analysis set.

Data obtained until progression, or last evaluable assessment in the absence of progression, will be included in the assessment of CRR, regardless of whether the participant withdraws from therapy. Participants who discontinue treatment without a response, receive subsequent anti-lymphoma therapy and then respond will not be included as responders in the CRR.

The CRR will include data of all scans, regardless of whether it was scheduled or not.

The CRR will be presented by the number and percentage of participants with CR including 95% cIs based on exact binomial proportions.

The CRR as assessed by BICR based on Modified Lugano criteria for lymphoma is the primary efficacy endpoint in Cohort B2 in Dose Expansion. The CRR is a secondary endpoint for Part A Dose Escalation assessed by Investigator based on Modified Lugano criteria and RECIL criteria.

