- Baseline is the last non-missing value obtained prior to the first dose/administration of any study treatment and any information taken after first dose/administration of study treatment is regarded as post-baseline information. If two visits are equally eligible to assess participant status at baseline (eg. screening and baseline assessments both on the same date prior to first dose/administration with no washout or other intervention in the screening period), the average is taken as the baseline value. For non-numeric laboratory tests (ie, some of the urinalysis parameters) where taking an average is not possible then the best value is taken as baseline as this is the most conservative. In the scenario where there are two assessments on Day 1 prior to first dose, one with time recorded and the other without time recorded, the one with time recorded is selected as baseline. Where safety data are summarized over time, study day is calculated in relation to date of first treatment. For assessments on the day of first dose where time is not captured, a nominal pre-dose indicator, if available, serves as sufficient evidence that the assessment occurred prior to first dose. Assessments on the day of the first dose where neither time nor a nominal pre-dose indicator are captured is considered prior to the first dose if such procedures are required by the protocol to be conducted before the first dose. If no value exists before the first dose/administration, then the baseline value is treated as missing.
- In all summaries, change from baseline endpoints will be calculated as the post-treatment value minus the value at baseline. The percentage change from baseline will be calculated as (post-baseline value baseline value) / baseline value × 100. For any endpoint subjected to log transformation, the change from baseline calculated and summarized on the log scale will be back-transformed and presented as a 'baseline scaled ratio' (BSR). Percentage change will be then calculated as (BSR 1) × 100.
- Unless stated otherwise, two-sided confidence intervals are produced at 95%.

– ed. 3.0

- For the purposes of summarizing safety data assessed at visits, in addition to baseline
 data, only on treatment data will be included in the summary tables. On treatment
 data will be defined as data after the first dose of IP and with assessment date up to
 and including the date of last IP + 90 days, and prior to the start of any subsequent
 cancer therapy.

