4.2.2.2 Primary Analysis of Primary Endpoint: ORR

Summaries will be produced that present the number and percentage of participants with a response (CR/PR) based upon the number of participants in the response-evaluable analysis set. ORR will be presented with 95% CI based on exact binomial proportions.

BoR will be summarized by number of participants and percentage for each category (CR, PR, MR [for RECIL criteria], SD, PD, and NE). No formal statistical analyses are planned for BoR.

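### SAP Table 2 gives the Part A objective response rate an 80% interval, against 95% in the section it cites, in the protocol and in the adjacent CRR row

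*Protocol*

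**What the plan says.** **Analysis text, ORR.** Protocol 9.4.2.1 says "The ORR will be presented by the number and percentage of participants with a response (CR/PR) including 95% cIs based on exact binomial proportions". The same subsection names ORR as the primary efficacy endpoint of Cohort B1 and as a secondary endpoint of Part A. SAP 4.2.2 opens with the same two uses, and SAP 4.2.2.2 says "ORR will be presented with 95% CI based on exact binomial proportions".

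**Analysis text, CRR.** Protocol 9.4.2.1 says "The CRR will be presented by the number and percentage of participants with CR including 95% cIs based on exact binomial proportions", and SAP 4.2.3.2 also specifies exact two-sided 95% intervals.

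**Defaults.** Protocol 9.4.1: "Unless stated otherwise, two-sided cIs will be produced at 95" per cent. SAP 3.3.1: "Unless stated otherwise, two-sided confidence intervals are produced at 95" per cent.

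**SAP Table 2.** The rows for B1 ORR, B2 CRR and Part A CRR all give 95%. The Part A ORR row gives 80% and points to section 4.2.2. The end of that cell did not read cleanly in the text available, but the 80% is legible.

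**Changes from protocol.** SAP section 2 marks these as not applicable.

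**Planning tables.** Protocol 9.2, Part B Dose Expansion: "Observable exact binomial two-sided 80% cIs are presented in Table 19 and Table 20". Both table titles repeat the 80%. The same paragraph says that the Part B size was chosen mainly to keep the No-Go decision accurate.

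**The concern.** Two explicit instructions for one endpoint disagree. A programmer working from SAP Table 2 would produce 80% limits for Part A ORR; one working from SAP 4.2.2.2 would produce 95% limits. The defaults do not settle it, because both yield to a specific statement and here the specific statements conflict.

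The Part A outputs are shown by dose level, with ORR and CRR on the same participants. An ORR interval at 80% beside a CRR interval at 95% would make ORR look better determined only because of the level chosen. The ambiguity could also spread: the SAP text after Table 2 says that the supportive investigator-assessed analyses for Part B follow what is done for Part A.

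**Working it through.** **Step 1. Set the sources side by side.**

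| Source | Endpoint | Level |
|---|---|---|
| Protocol 9.4.2.1 | ORR (B1 primary, Part A secondary) | 95% |
| Protocol 9.4.2.1 | CRR (B2 primary, Part A secondary) | 95% |
| SAP 4.2.2.2 | ORR | 95% |
| SAP 4.2.3.2 | CRR | 95% |
| SAP Table 2 | B1 ORR | 95% |
| SAP Table 2 | B2 CRR | 95% |
| SAP Table 2 | Part A CRR | 95% |
| SAP Table 2 | Part A ORR | **80%** |

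One entry differs from all the others.

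**Step 2. Size of the difference in Part A.** SAP 3.3.7.2 gives 3 to 12 participants for the mTPI-2 cohorts. SAP 3.3.1 says that dose levels with one participant are only listed, so no interval arises there. The exact limits for x responders of n at confidence 1 − α are

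- lower = α/2 quantile of Beta(x, n − x + 1)
- upper = 1 − α/2 quantile of Beta(x + 1, n − x)

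with α = 0.20 or 0.05. The response counts below are illustrative.

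| x/n | 80% interval (width) | 95% interval (width) | Width ratio | 80% narrower by |
|---|---|---|---|---|
| 1/3 | 3.5 to 80.4 (77.0) | 0.8 to 90.6 (89.7) | 0.858 | 14% |
| 2/6 | 9.3 to 66.7 (57.4) | 4.3 to 77.7 (73.4) | 0.782 | 22% |
| 4/12 | 15.4 to 55.9 (40.5) | 9.9 to 65.1 (55.2) | 0.734 | 27% |

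The range of 14 to 27% applies to observed rates of about one third. With no responders the lower limit is 0 and the upper limit is 1 − (α/2)^(1/n). At n = 12 that is 1 − 0.10^(1/12) = 17.5% against 1 − 0.025^(1/12) = 26.5%, a ratio of 0.66, so 34% narrower.

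**Step 3. Do Tables 19 and 20 share the fault?** Their counts and limits are redacted, so the printed figures cannot be reproduced; only the level can be examined. The footnote to protocol Table 22 gives the B1 rule: No-Go if P(ORR > 40%) < 10%. Protocol 9.5.1 gives the prior Beta(1,1), so the posterior is Beta(1 + x, 1 + n − x). A two-sided 80% interval leaves 10% in each tail. With n = 100, the B1 total printed in protocol 9.2:

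- x = 33: P(ORR > 40%) = 0.079, No-Go; upper 80% limit 39.7%, below 40%.
- x = 34: P(ORR > 40%) = 0.115, not No-Go; upper 80% limit 40.8%, above 40%.

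The match is close but not an identity. At an assumed n = 88, No-Go is met up to x = 29, where the upper 80% limit is 40.2%.

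**Step 4. Width at the Part B sizes, for information.** At 40/100 the 80% interval is 33.4 to 46.9 (width 13.5) and the 95% interval is 30.3 to 50.3 (19.9). The ratio is 0.675, so 32% narrower. For B2 the size is redacted; at an assumed n = 40, 16/40 gives 29.4 to 51.4 against 24.9 to 56.7, a ratio of 0.690. Over assumed sizes of 20 to 100 the 80% interval is 29 to 32% narrower.

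**The case against.** The other side can say that this is one cell for one secondary endpoint, that the detailed text would normally govern, and that no dose rule uses the interval. Protocol 6.6.5 bases the OBD on safety, efficacy, PK, pharmacodynamic and biomarker data, and the RP2D on the totality of the escalation data, with no threshold on a confidence limit. All of that stands and limits the consequence. It does not remove the contradiction, because neither document says whether the table or the text prevails.

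A reader might infer more: that Tables 19 and 20 overstate precision by about a third, because the primary endpoints will be reported at 95%. The documents do not support that. The tables say 80% in the text and in both titles, and claim nothing at 95%. Both 95% defaults allow a stated exception, and protocol 9.2 states one. The Part B size is justified by No-Go accuracy, protocol 9.1 plans no formal hypothesis test, and for B1 the 80% level lies close to the decision rule. The figure of about a third is right as a comparison of widths at the Part B sizes. It describes a choice of level, not an error, and it does not carry over to Part A cohorts at response rates near one third.

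A reader might also infer that the primary results have two competing intervals. They do not: B1 ORR and B2 CRR are at 95% throughout the analysis text and in SAP Table 2.

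**Conclusion.** The SAP contradicts itself and the protocol on the confidence level for Part A ORR. If the table were followed, the intervals would be about 14% narrower than planned at 1/3, 22% at 2/6 and 27% at 4/12 (up to 34% at 0/12), and not comparable with CRR on the same participants. The conflict is plain from the text and rests on no assumption; the sizes rest on exact binomial limits and illustrative counts within the stated cohort sizes.

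The point stops there. The sample size is not shown to be wrong, the planning tables are correctly labelled, and the primary response endpoints are unaffected. The agreement between 80% and the No-Go rule was checked for B1 only and uses n = 100 from protocol 9.2; the corresponding figure in protocol 4.1.2 is blank, and the B2 threshold is redacted.

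**What to change.** Change the Part A ORR row of SAP Table 2 to a 95% CI. If an 80% interval is wanted there as well, label it as additional and give the reason. This costs one table cell and no new analysis.

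Optionally, add a labelled 95% row to protocol Tables 19 and 20, or one sentence in 9.2 explaining why 80% is shown, so that readers can see the precision at the reporting level. The cost is a recalculation of two tables or one sentence; the design does not change.

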# Table 19Estimated Response Rate and 80% Two-sided Confidence Interval Out
of Participants (Cohort B1)

Number (%) of Objective Responses a	(20%)	(25%)	(30%)	(35%)	(40%)	(45%)
CCI	CCI	CCI	CCI	CCI	CCI	CCI
CCI	CCI	CCI	CCI	CCI	CCI	CCI

a Objective response per Modified Lugano Criteria (objective response rate for Cohort B1).
 b CI obtained from exact binomial distribution.

Abbreviation: CI: confidence interval.

